7.1.2 Timing of assessments

Relevant timing is as detailed above in Section 7.1.1 (notations immediately below table).

7.1.3 Medical history

Medical history findings (i.e. previous diagnoses, diseases or surgeries) meeting all criteria listed below will be collected:

1. Not pertaining to the study indication
 - Start before signing of the informed consent
 - Considered relevant to the study

Detailed instructions on the differentiation between (i) medical history and (ii) adverse events can be found in Section 7.15.1.1.

7.2 ^{99m}Tc MDP bone scan: Standard clinical bone scan will be carried out per institutional practice.

7.3 CT a/p: Standard clinical CT of the abdomen and pelvis will be carried out per institutional practice.

7.4 Medication history: Medication history, including any changes in medication use since last assessment, will be reviewed.

7.5 Chemistry panel: Standard comprehensive metabolic panel (including sodium, potassium, chloride, bicarbonate, BUN, creatinine, glucose, total protein, albumin, AST, ALT, total bilirubin, direct bilirubin, and alkaline phosphatase) will be carried out at the MGH clinical laboratory in real time.

7.6 CBC with differential: Standard comprehensive metabolic panel (including white blood cell count, hemoglobin, hematocrit, platelets, and differential) will be carried out at the MGH clinical laboratory in real time.

7.7 PSA: Standard PSA assay will be carried out at the MGH clinical laboratory in real time.

7.8 Fluciclovine PET/MRI: This testing will be carried out only for 10 study participants. They will be chosen by investigator discretion in light of their willingness and medical eligibility to undergo PET/MRI (e.g. pacemaker is a contraindication, claustrophobia is a contraindication). The agent used in this study will be the radiolabeled agent (fluciclovine) that will be administered prior to standard whole body PET imaging which includes skull base to thigh. Fluciclovine will be handled by qualified personnel, familiar with procedures that minimize undue exposure to themselves and the environment. PET/MRI imaging will be carried out per standard/clinical institutional protocol. Thus far, there is limited experience using fluciclovine PET/MRI; it is investigational.

7.9 CTCs by CellSearch (see Appendix G for detailed instructions):

At study-designated timepoints, 7.5 mL of whole blood will be collected in a special CellSave tube (available from Veridex/Janssen Diagnostics), which is then stored at room temperature until processed. It will be sent to the BWH CTC Lab for analysis. The BWH Circulating Tumor Cell Laboratory provides circulating tumor cell (CTC) services using the Veridex/Janssen Diagnostics CellSearch immunomagnetic platform. The lab is located to a CLIA-approved space within the BWH Cytology Division (Brigham and Women's Hospital, Medical Research Building, 3rd Floor; [name]). **Major equipment includes the** CellSearch Autoprep, and CellTracks Analyzer II. The CTC Lab provides clinical enumeration of CTCs for patients with metastatic prostate cancer using the FDA-cleared Veridex/Janssen Diagnostics CellSearch System. It also functions as the BWH CTC Core Lab

(http://www.partners.org/researchcores/CTC/CTC_BWH.html) providing enumeration and isolation of CTC for research purposes. The current director is [name]. (**[contact], **[contact], **Email:** [contact]).

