Functional imaging of neoplasms using PET/CT has become an integral part of evaluation of a diverse group of malignancies. ^{18}F -fluoro-deoxyglucose (^{18}F -FDG) is the most widely used PET tracer in oncology but has not been useful in prostate cancer due to inadequate sensitivity as well as intense PET signal in the bladder due to renal elimination. Anti-1-amino-3-fluorine 18-fluorocyclobutane-1-carboxylic acid (FACBC; now known as fluciclovine) PET is an alternative PET tracer that is an L-leucine analog and has demonstrated promising sensitivity and specificity for the detection of prostate cancer.²¹⁻²³ Fluciclovine was approved by the FDA in 2016. Since fluciclovine uptake depends on the tumor cells themselves and not on physiological response of adjacent bone or lymph tissue, detection based on fluciclovine PET imaging is effective for soft tissue, lymphatic, and osseous metastases. We hypothesize that quantitative assessment of bone tumor volume as assessed by fluciclovine PET will reveal a decrease after 8 weeks of Ra-223 treatment.

Further, we expect that this study will establish fluciclovine PET as an imaging biomarker of Ra-223 activity for potential use in future trials and in clinical practice.

Circulating Tumor Cells

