7.1 Schedule of procedures

7.1.1 Tabulated overview

Table 1: Treatment	S	B	T1 D 1	T1 D 4	T 2	T3	T 4	T 5	T 6	F/ U 1M	F/ U 4M	F/U 18 M
History & physical exam	X		X		X	X	X	X	X	X	X	X
^{99m} Tc MDP bone scan	X					X ¹					X	
CT a/p	X					X ^{1, 2}					X	
Fluciclovine PET/MRI ³		X				X ¹						
Medication history	X		X		X	X	X	X	X	X	X	X
Chemistry panel	X		X		X	X	X	X	X	X		
CBC with differential	X		X		X	X	X	X	X			
PSA			X		X	X	X	X	X	X	X	X
CTCs by CellSearch ⁴			X		X	X						
CTCs by microfluidic chip ⁵				X		X	X					
BAP & NTx			X	X	X	X	X	X	X	X	X	X
Blood biomarkers ⁶			X	X	X	X	X	X	X	X	X	X
Patient reported outcomes ⁷				X		X	X	X	X	X	X	X
Adverse event reporting				X		X	X	X	X	X		

Notations:

Screening studies “S” must be done within 60 days of start of treatment (“T1 D1”).

Baseline study “B” must be done after a subject is successfully registered to the trial, but prior to start of treatment (“T1 D1”).

Treatments T1 through T6 occur at 4 week intervals \pm 7 days.

(1) T3 timepoint scans (bone scan, and CT a/p, and fluciclovine PET/MRI in some) will be performed within 10 days prior to the T3 treatment day.

(2) T3 timepoint CT a/p will be performed only for participants that do not undergo fluciclovine PET/MRI.

(3) fluciclovine PET/MRI will be performed at two timepoints each for 10 of the study participants. They will be chosen by investigator discretion in light of their willingness and medical eligibility to undergo PET/MRI (e.g. pacemaker is a contraindication, claustrophobia is a contraindication). The baseline PET/MRI will only be done after the subject has successfully been registered to the trial, but prior to start of treatment (“T1 D1”).

(4) CTCs, circulating tumor cells; 7.5 mL of whole blood will be collected in a special CellSave tubes as described in Appendix G for BWH core lab testing using the commercially available Veridex CellSearch assay; subsequent CTC testing will only be carried out on participants who had ≥ 1 detectable CTC on study T1 D1.

(5) 20 mL of blood will be collected in vacutainer tubes (usually purple top EDTA tubes) for [name]/[name] laboratory analysis of circulating tumor cells as detailed in Appendix B;

subsequent CTC testing will only be carried out on participants who had ≥ 1 detectable CTC on study T1 D1.

(6) Plasma biomarkers; 10 mL of blood will be collected in a purple top (EDTA plasma) tube and processed as detailed in Appendix C for batched analysis of inflammatory and angiogenic biomarkers.

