7.16 Other procedures and variables

7.17 Appropriateness of procedures / measurements

The assessments described in the previous sections are widely used and generally recognized as reliable, accurate, and relevant for determining the safety and efficacy of therapies in this disease.

8. Statistical methods and determination of sample size

Primary Aim

“The values in this protocol have been revised as per the United States (US) National Institute of Standards and Technology (NIST) standardization update (agreed on 17 MAR 2015)”

Bone scan response is defined as a $\geq 30\%$ decrease in quantitative bone scan lesion area (BSA) from baseline to the end of month 2 of Ra-223 treatment (i.e. after 2 of 6 possible Ra-223 doses). In a one-stage design, 22 subjects will be enrolled to evaluate the primary endpoint of bone scan response. Assuming 90% of subjects with adequate data, the evaluable sample size is 20 subjects. With 20 subjects, given target power of 90% and 1-sided 5% alpha, a null hypothesis of $\leq 10\%$ versus an alternative hypothesis of $\geq 35\%$ in the proportion of patients achieving response can be evaluated. If 5 or more responses are observed in 20 subjects, this method of response assessment will be considered promising.

Operating characteristics

Probability of ≥ 5 responses in 20 pts	True but unknown rate of Bone Scan Response Rate					
	10%	15%	20%	25%	30%	35%
Probability of ≥ 5 responses in 20 pts	0.04	0.17	0.37	0.59	0.76	0.88

Secondary Aims

A key secondary objective is to evaluate whether quantitative analysis of ^{99m}Tc -MDP bone scan after 2 months of therapy can identify patients who will achieve long term clinical benefit. Towards this end, all subjects will be treated and followed for at least 18 months. Survival status at 18 months will be ascertained (i.e. dichotomized as survivor or non-survivor at 18 months). A two-sample t-test will be used to determine the difference in mean percent change in BSA between survivor and non-survivor groups. Reported median survival for the study cohort of the ALSYMPCA trial was 14.9 months. Assuming events follow an exponential distribution this parallels an 18-month survival rate of 43%. The detectable difference will depend on the variability in change in BSA as measured by standard deviation (SD). There is 80% power to detect an effect of 1.332 SD given a 2-sided 0.05 alpha and 20 evaluable patients divided as 9 survivors and 11 non-survivors.

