Bone scans are scheduled for the beginning of month 3/end of month 2 (T3), and one month post month 6 (FU1M). Descriptive statistics on absolute and percent change in BSA from baseline to these study timepoints will be provided for the overall study cohort and within survivor groups. By the end of month 2, bone scan response is expected in 35% of subjects. Patients will be cross-classified by bone scan response status at 2 months and survival status at 18 months. Agreement will be quantified using Cohen's Kappa; however, the sample size is too small to produce a realistic confidence interval. Kappa is assessed as follows: <0.00, poor; 0.00-0.20, slight; 0.21-0.40, fair; 0.41-0.60, moderate; 0.61-0.80, substantial; 0.81-1.00, almost perfect; and 1.00, perfect. Survival time defined as the time from registration to death, or if censored to date last known alive will be calculated. Correlation between change in BSA after 2 months and survival time will be assessed graphically with scatter plots and using Pearson correlation coefficient. Survival distributions will also be estimated using the Kaplan-Meier method in a landmark analysis at 2 months. Survival time is defined as the time from response classification (at 2 months) to death, or if censored to date last known alive. Cox proportional hazards (PH) regression will be used to estimate the bone scan response hazard ratio along with 95% confidence limits.

This study also affords insights into several other potential biomarkers including measures related to circulating tumor cells (number, proliferative index, AR signaling, markers of DNA damage/repair), bone turnover (BAP, NTx), inflammation and angiogenesis. Fluciclovine PET imaging will occur in 10 subjects at baseline and the end of month 2 of treatment. All other measures will occur at baseline, during treatment, and post treatment as detailed in the required data table. Descriptive statistics will be provided for each measure and timepoint along with absolute and percentage change from baseline. Association with overall survival and response will be analyzed as exploratory similar to the methods above for bone scan.

Accrual Targets

Accrual Targets						
Ethnic Category	Sex/Gender					
	Females		Males		Total	
Hispanic or Latino	0	+	1	=	1	
Not Hispanic or Latino	0	+	21	=	21	
Ethnic Category: Total of all subjects	0	(A1)	+	22	(B1) = 22 (C1)	
Racial Category						
American Indian or Alaskan Native	0	+	0	=	0	
Asian	0	+	1	=	1	

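### The 10 PET/MRI men are chosen at investigator discretion with no ordering rule, so the only fluciclovine data may not represent the 22-man cohort

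*Combined protocol and SAP*

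**What the plan says.** Section 7.8 restricts PET/MRI to 10 participants and gives one rule for who they are: "They will be chosen by investigator discretion in light of their willingness and medical eligibility to undergo PET/MRI". Its examples of ineligibility are "pacemaker is a contraindication, claustrophobia is a contraindication". Note (3) under the schedule in Section 7.1.1 repeats the rule ("They will be chosen by investigator discretion in light of their willingness and medical eligibility") and adds that "fluciclovine PET/MRI will be performed at two timepoints each for 10 of the study participants".

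On timing, note (3) states: "The baseline PET/MRI will only be done after the subject has successfully been registered to the trial, but prior to start of treatment". The schedule puts the history and examination, bone scan, CT, chemistry panel and blood count at screening.

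Note (2) gives the T3 CT only to men who do not have PET/MRI. Sections 2 and 4 speak of men being assigned to PET but describe no assignment procedure.

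For analysis, Section 8 says "Fluciclovine PET imaging will occur in 10 subjects at baseline and the end of month 2 of treatment". It plans descriptive statistics with absolute and percentage change from baseline, and labels associations with survival and response exploratory. Section 1.1 is more ambitious: "we expect that this study will establish fluciclovine PET as an imaging biomarker of Ra-223 activity", with later trials and clinical practice in view.

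**The concern.** Willingness and MRI contraindications are legitimate limits on who can be scanned. If more than 10 men pass both, however, only the investigator's judgement decides among them, and by then the investigator can see each man's screening results. Eligibility is broad (ECOG 0 to 2, at least two bone metastases, nodal disease allowed), so there is room for the chosen men to differ from the rest. Each PET man also needs a second scan before T3, which gives a practical reason to prefer men who look likely to reach it.

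Two things are at stake. The first is whether PET change in these 10 men, and its relation to bone scan response and survival, describes the whole cohort. Without a log or a planned baseline comparison, a reader of the results could not judge this. The second is the T3 CT. CT is a named secondary imaging measure in Section 2, but T3 PET and T3 CT will come from two separate groups of men, divided by the same discretionary choice.

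**Working it through.** **The plan's own figures.** No sample-size argument is given for the 10 PET men. The main calculation is for the primary endpoint ("22 subjects will be enrolled to evaluate the primary endpoint of bone scan response", 20 evaluable, 5 or more responses considered promising). With X binomial (20, p):

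- P(X ≥ 5) at p = 0.10 is 0.043 (plan: 0.04).
- P(X ≥ 5) at p = 0.35 is 0.882 (plan: 0.88).

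Both reproduce. PET is not an input to either, so the choice of PET men cannot change them.

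**Share selected.** 10/22 = 45%. This is the size of the subset and says nothing about the size of any bias. At most 22 − 10 = 12 men can have a T3 CT.

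**What the selection can and cannot depend on.** Screening results come before registration, and registration comes before the baseline PET/MRI, so screening findings can influence the choice. The baseline PET/MRI comes before the first Ra-223 dose, so entry to the subset cannot depend on any on-treatment result.

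**How large a shift could be.** The documents give no figure for selection behaviour, so both ranges below are assumptions.

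1. *Mean PET change.* Let f = 10/22 be the fraction chosen and r the correlation between being chosen and PET change. The chosen men's mean differs from that of all 22 by r × √((1 − f)/f) SD. Here √((12/22)/(10/22)) = √1.2 = 1.095.
   - r = 0.1 gives 0.11 SD.
   - r = 0.2 gives 0.22 SD.
   - r = 0.3 gives 0.33 SD.
   - For comparison, the standard error of a mean at n = 10 is 1/√10 = 0.32 SD.

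2. *Share of bone scan responders in the subset.* Section 8 expects 35% to respond: 0.35 × 22 = 7.7, taken as 8 men (36%). An unselected 10 would contain 36% responders on average. If the odds of being chosen were 1.5, 2 or 3 times higher for men who go on to respond, the expected share (Fisher's noncentral hypergeometric distribution) would be 42%, 45% or 51%.

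**Precision at n = 10.** A paired test at two-sided 0.05 has 80% power only for a mean change of about 1.00 SD. An observed 4 of 10 has an exact 95% interval of 12% to 74%. Sampling error is therefore about as large as the assumed shifts or larger. A confidence interval expresses sampling error but does not reveal a selection shift.

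**The case against.** The strongest reply is that discretion is tied to willingness and medical eligibility, and that on a natural reading those are its only grounds. A consecutive series would be filtered by both as well, and entry to the whole trial already rests partly on investigator judgement. PET lies outside the primary endpoint and every powered test, the study calls itself exploratory, and 10 men limit PET inference at least as much as the manner of choosing them. The baseline data for a PET versus non-PET table are already scheduled, since every man has a screening bone scan and a T1 D1 PSA.

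Most of this stands, and it rules out three stronger readings that a reader might infer.

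- *The investigators hand-pick men freely.* The text ties their discretion to stated grounds, and nothing in it describes steering by fitness or disease burden. What is missing is a rule for ordering the men who qualify.
- *The fluciclovine response estimate is biased by selection on outcome.* Men enter the subset before treatment and PET change is measured within patient, so the documents show no route for this.
- *The PET results cannot be generalised at all.* The documents support only that representativeness is uncertain and, as planned, could not be judged.

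The reply does not explain why no order and no log are specified, and it does not address the T3 CT, which the same choice allocates. Nor does pre-treatment selection protect the exploratory associations with survival, because fitness and disease burden are plausibly prognostic.

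**Conclusion.** The point holds as a minor one about representativeness. The selection rule leaves the order among willing, eligible men to discretion exercised when screening results are available. The resulting 10 of 22 men are the only source of fluciclovine data and, by exclusion, determine who has a T3 CT.

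The primary endpoint, its error rate and its power are unaffected. The documents do not allow the size of any distortion to be estimated. The 0.11 to 0.33 SD shifts rest entirely on assumed correlations of 0.1 to 0.3, and the 42% to 51% responder shares on assumed odds ratios of 1.5 to 3. If 10 or fewer men turn out to be willing and eligible, discretion has nothing left to decide and only the effect of those two filters remains.

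The point gains weight from the Section 1.1 expectation that the study will establish the tracer as a biomarker. The descriptive and exploratory analysis in Section 8 could not support that claim from 10 men, however they were chosen.

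**What to change.** - **Section 7.8 and note (3) of Section 7.1.1:** replace the discretion sentence with a rule that PET/MRI is offered, in order of registration, to each man without a contraindication until 10 have accepted.
- **Log:** for each man not scanned, record whether he declined, had a contraindication (and which), or registered after the subset was full.
- **Section 8:** add a table of baseline BSA and PSA for PET versus non-PET men, to be read alongside the PET results and the T3 CT results.
- **Section 1.1:** soften *establish* to wording that fits an exploratory analysis, for example that the study may support further evaluation of fluciclovine PET as a candidate biomarker.

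The cost is some loss of freedom in scheduling the scanner, plus a short log. Men taken in order may also be somewhat less likely to complete the second scan than men picked for convenience, so the number of complete pairs should be reported. The subset stays at 10, no scans are added, and no stated design figure changes. If some of the 10 have already been scanned, the rule and log can apply to the remaining places and the baseline table can still cover everyone.

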7.10 CTCs by microfluidic chip: (see Appendix B for detailed instructions)

Two 10 mL samples of peripheral blood will be collected into vacutainer tubes (Becton-Dickinson) containing the anticoagulant EDTA. Samples will be shipped by U.S. Ground courier to the MGH Charlestown Navy Yard laboratories of Drs. [name] and [name]. Alternatively, a member of the [name] or [name] labs will personally transport the samples from the MGH Cancer Center to the MGH Charlestown Navy Yard laboratories. Samples will be processed through the experimental platform within 6 hours of collection, according to previously established protocols^{52,53} with modifications subject to current lab protocol. Briefly, a 5 mL aliquot of blood will be placed into an air-tight conical tube on a rocker assembly, and blood will be pneumatically driven through the microfluidic chip at a protocol-specified flow rate. The microfluidic chip will then be flushed with phosphate-buffered saline at a protocol specified flow rate to remove nonspecifically bound cells. CTCs on the chip will be fixed, permeabilized, and stained with antibodies. Staining for PSA, PSMA, DAPI, Ki-67, and other proteins will be performed. Captured CTCs will then be identified and enumerated using the automated detection system as previously described⁵². RNA and/or DNA will also be isolated from CTCs captured on a separate chip for gene expression analyses. Any remaining isolated RNA or DNA will be stored frozen at -70 to -90 degrees C for batch global profiling analyses. See Appendix B additional processing instructions.

7.11 Bone turnover markers (see Appendix H for detailed instructions):

Sera will be collected from subjects at study-specified timepoints. It will be processed and stored as detailed in Appendix H. Serum N-telopeptide concentrations will be determined at a Massachusetts General Hospital core laboratory using a competitive inhibition enzyme-linked immunosorbent assay (ELISA/EIA) (Osteomark® NTx Serum, Alere Scarborough, Inc., Scarborough, ME). The intra-assay and inter-assay variability are 4.6% and 6.9%, respectively. Quantitative bone-specific alkaline phosphatase (BAP) will be determined at a Massachusetts General Hospital core laboratory using an enzyme immunoassay (MicroVue™ BAP EIA; Quidel Corporation, San Diego, CA).

7.12 Blood biomarkers (see Appendix C for detailed instructions):

Blood samples will be collected at study specific timepoints. For the purposes of this testing, at least 10 mL will be collected in a PURPLE top (EDTA plasma) tube. After processing, separated peripheral blood cells will be immediately

stained using fluorescently labeled antibodies and analyzed using an LSR-II flow cytometer within the Steele Laboratory's facility. [name], D.M.D., Ph.D. (Associate Professor at MGH/HMS), who has over 12 years of experience in clinical correlative studies, supervises the Steele Lab's Core operation. Plasma analysis will be carried out for a panel of circulating angiogenic and inflammatory molecules. They include vascular endothelial growth factor (VEGF), placental-derived growth factor (PIGF), soluble (s)VEGFR1, basic fibroblast growth factor (bFGF), VEGF-C, VEGF-D and sTie2 using multiplex (7-plex) and IL-1 β , IL-6, IL-8 and TNF- α (4-plex) protein array kits from Meso-Scale Discovery (Gaithersburg, MD), and stromal cell-derived factor 1a (SDF1a), hepatocyte growth factor (HGF), soluble (s)c-MET, and s-c-KIT using ELISA from R&D Systems (Minneapolis, MN). Finally, we will evaluate biomarkers of tumor hypoxia, by measuring plasma carbonic anhydrase IX (CAIX) levels as well as biomarkers of osteoclast and osteoblast activity (plasma C-telopeptide and total alkaline phosphatase) using ELISA from R&D Systems. Samples will be run in duplicate.

7.13 Patient reported outcomes: Key patient reported outcome measures will include:

1. Analgesic use as recorded in a medication diary (see Appendix D)
2. Changes in quality of life as measured by a validated assessment tool (EQ-5D-3L; see Appendix E)
3. Changes in pain and narcotic analgesic use as assessed by 4-item questionnaire taken from the MD Anderson Brief Pain Inventory (BPI; see Appendix F)⁵⁴:
 - A. Pain at its worst in the last 24 hours (BPI question 3)
 - B. Average pain in the last 24 hours (BPI question 5)
 - C. Effect of pain on general activity (BPI question 9A)
 - D. Effect of pain on sleep (BPI question 9F)

